5.3 Informed Consent Procedures

Providers

Waiver of written documentation of informed consent for provider participation. Providers who order lung cancer screening tests are the target for this pragmatic study. Based on recent estimates of lung cancer screening participation at VA NY Harbor and VA Providence, approximately 300 providers have ordered lung cancer screening procedures for 2000-4000 Veterans. The purpose of the pragmatic trial is to test a structured approach to supporting providers to better integrate smoking cessation as part of reporting screening results to patients. A high level of participation of all VA providers who order lung cancer screening tests is critical to this pragmatic trial as the goal is to answer if this structured support is both feasible to implement and effective at improving patient outcomes. We have designed an opt-out approach to help lead to a wide range of provider participation, as requiring providers to opt-in to study participation would potentially bias the results or make them generalizable only to a small subset of providers and not VA overall.

We will send all primary care providers who are ordering lung cancer screening tests a letter and Information Sheet in the postal mail to their office mailing address. We will then send a copy of the letter and Information Sheet via email, and finally follow up via Lync/Skype for Business (instant message, with link to Information Sheet and invitation letter in PDF format attached). In each communication, we will make clear that if we do not hear back from them, they will be enrolled in the study.

Patients

A Waiver of Informed Consent is requested for administrative medical record review of historical provider screening volumes. In order to ensure balance in randomization by provider volume (as some providers order hundreds of screening CTs per year and other providers order only one or two), we are requesting access to patient screening data between 1/1/2013 and 12/31/2017. We will need to access thousands of records in the Corporate Data Warehouse as NY Harbor and Providence have screened an estimated 2000-4000 Veterans. It is impracticable to obtain consent for all patients in the database, and the risk for loss of confidentiality is minimal.

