5.6 Data Analysis

Sample size determination. Our target sample size of 270 respondents per arm with complete 12-month outcome information was selected to have sufficient (80%) power to detect a doubling of abstinence rates (Relative Risk = 2) using a multilevel random effects model with patients clustered by randomized provider. The assumed intraclass correlation coefficient for the provider clustering effect is assumed to be 0.01. Power is based on a two-sided test with type-1 alpha error rate of 0.05%. Due to randomization, we do not anticipate needing to adjust for patient covariates.

Intent-to-treat (ITT) analysis We will utilize an intent-to-treat approach and include all participants who meet study eligibility criteria and are assigned to a study arm, regardless of whether they participated in all of the care components of that arm (e.g. declined proactive telephone counseling). Our primary analysis will focus on participants for whom we have complete 12-month abstinence (target n=270 per arm).

Missing outcome data. For secondary analyses, we will examine outcomes for all eligible screening patients who are current smokers offered screening by a participating randomized provider during the study period. This analysis will include patients who do not participate in the survey assessment of cessation outcomes. We will perform two secondary analyses. The first will assume that patients who do not participate in the survey assessment (e.g. missing abstinence outcomes) will be considered continued smokers, which is a typical intent-to-treat approach for cessation trials. We do not anticipate differential missing data across study arms. Second, we will address potential missing cessation data by requesting a HIPAA waiver and waiver of informed consent to review EMR data for all eligible patients to estimate an administrative assessment of cessation, based on HealthFactors data and whether patients report quitting at a subsequent visit or when they return for annual lung cancer screening. The methods developed by McGinnis et al, will be used to construct this administrative cessation variable.

(Note, due to COVID pandemic changes in lung cancer screening utilization and study enrollment timelines, the missing data protocol using EMR data was adapted for the primary outcome. See the Statistical Analysis Plan.)

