
• Current smoker• Participant in lung cancer screening	
• Patients with urgent findings requiring biopsy/immediate attention on the screening CT• Patients with a prior diagnosis of lung cancer or who are receiving active therapy for any cancer other than skin cancer• Patients previously diagnosed with cognitive impairment, dementia, or severe behavioral disorders• Patients who have an indication in chart review of difficulty communicating or participating in telephone counseling sessions

4. Sampling and Randomization

This is a cluster randomized two-arm parallel group trial. Randomization occurred at the provider-level. Lists of providers referring patients to lung cancer screening at Study Site A & Study Site B were

prepared. Providers at each site were pair-matched on patient volume and then randomized to either the intervention arm or the control arm. Randomization was performed using random numbers generated with the R programming language.

Following randomization, all patients of enrolled providers who attended lung cancer screening and met eligibility criteria were considered enrolled in the study, with treatment arm corresponding to the randomized treatment arm of their provider.

5. Study Outcome Measures

					Assessment Timepoint
Measure (Units)	Comments	Data Type	BL	3M ¹	12M
Primary Outcome (1)					
Self-reported smoking cessation at 12 months	Constructed from 12-month survey and EMR data	Binary			✓
Secondary Outcomes (3)					
Experience with Telephone Counseling	Survey only	Binary		✓	
Self-efficacy to quit	Survey only	Likert scale (0-10)		✓	✓
Motivational Assessment	Survey only	Likert scale (0-10)		✓	✓
Perception of susceptibility to harm	Survey only	Summary Score		✓	

6. Study Covariates

			Assessment Timepoint		
Measure (Units)	Comments	Data Type	BL	3M ¹	12M ¹
Treatment Assignment	Intervention or Control	Binary	✓		
Covariates for primary and secondary models (2)					
Site		Binary			
Additional covariates for primary and secondary sensitivity models (4)					
Additional variables collected²					
Gender	Self-report from screening and baseline questionnaires	Binary	✓		
Marital/partner status	Self-report from screening and baseline questionnaires	Categorical	✓		
Age	Self-report from screening and baseline questionnaires	Continuous	✓		
Highest level of education	Self-report from screening and baseline questionnaires	Ordinal	✓		

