Current employment status	Self-report from screening and baseline questionnaires	Categorical	✓		
Service connection	EHR	Binary	✓		
¹ Months post-LCS					

		Assessment Timepoint			
Measure (Units)	Comments	Data Type	BL	3M ¹	12M ¹

7. Statistical Analyses and Description of Main Tables

Aim 1 statistical analyses

The primary analysis will be an intent-to-treat based comparison of the two intervention arms. The analysis will be performed at the level of the individual. Clustering of patients within providers will be accounted for in the analysis by the inclusion of a random intercept for provider. The primary analysis will be based on the following random intercept logistic regression model

$$\text{logit}^{-1} \left(P(Y_{ij} | Treatment, Site) \right) = \beta_0 + \alpha_j + \beta_1 Treatment + \beta_2 Site$$

Where Y_{ij} is an indicator variable for whether the i^{th} patient of the j^{th} provider had quit smoking at 12 months, *Treatment* is a binary indicator for assigned treatment arm, and *Site* is a binary indicator for VA medical center (New York Harbor or Providence). The α_j represent random intercepts for each provider and are assumed to follow a common $N(0, \sigma^2)$ distribution. We will report point estimates and 95% confidence intervals for the odds ratio $\exp(\beta_1)$. Confidence intervals will be computed using bootstrap methods. A test of the null hypothesis of no association ($\beta_1 = 0$) will be performed using a likelihood ratio test. A p-value of less than 0.05 will be taken as sufficient evidence to reject the null hypothesis of no association.

Analyses for secondary outcomes will use models with similar predictor terms but with different link functions depending on the outcome. The table below describes model types in more detail for each outcome.

Analysis	Description	Outcome	Independent Variable(s)	Model type	Statistical Test
Primary outcome	Smoking cessation at 12 months	Indicator of smoking abstinence at 12 months	Binary treatment indicator; Binary site indicator; Categorical provider	Logistic regression with random intercept for provider	

Analysis	Description	Outcome	Independent Variable(s)	Model type	Statistical Test
			(clustering variable)		

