			(clustering variable)		
Secondary outcome	Perceived susceptibility to lung cancer	Score on susceptibility scale	Binary treatment indicator; Binary site indicator; Categorical provider (clustering variable)	Linear regression with random intercept for provider	

8. Handling of Missing Data

In descriptive statistics, we will describe the extent of missing data. We will examine whether there is differential missingness in outcomes across treatment arms and sites. We will assess the extent to which the distributions of patient characteristics differ between those with the primary outcome and those without the primary outcome.

Patients may have missing data due to survey non-response or missing EHR data. The primary analysis will be a complete-case analysis among those who have a smoking status at 12 months. In sensitivity analyses, we will adapt a method to examine the impact of non-ignorable missingness on the study's primary conclusions. We will use the following model, which incorporates a Missing Not at Random (MNAR) missingness mechanism through a sensitivity parameter representing the odds ratio of smoking cessation between people with missing outcomes and people without missing outcomes.

$$\text{logit}^{-1}(P(\text{Smoking})) = \beta_0 + \beta_1 \text{Tx} + \beta_2 \text{Site} + \beta_3 \text{Missing}$$

9. Project Links

Clinical Trials Website:

<https://clinicaltrials.gov/ct2/show/NCT03612804>

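### The MNAR sensitivity model in SAP section 8 leaves out the provider random intercept, so it ignores the randomised unit and does not reduce to the primary model; the effect is small at the planned ICC

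*SAP*

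**What the plan says.** - **Unit of randomisation.** SAP section 4 (Sampling and Randomization): "Randomization occurred at the provider-level". Each patient takes the arm of his or her provider.
- **Primary model.** SAP section 7: "Clustering of patients within providers will be accounted for in the analysis by the inclusion of a random intercept for provider". The equation is written out with patient and provider subscripts and a term α_j ~ N(0, σ²). Section 7 also names a likelihood ratio test and bootstrap intervals. In the table of analyses, every secondary row with a completed model type includes a random intercept for provider; the two quit-attempt rows are blank.
- **Primary analysis set.** SAP section 8: "The primary analysis will be a complete-case analysis among those who have a smoking status at 12 months".
- **Sensitivity analysis.** SAP section 8: "we will adapt a method to examine the impact of non-ignorable missingness on the study's primary conclusions", followed by "We will use the following model, which incorporates a Missing Not at Random (MNAR) missingness mechanism through a sensitivity parameter". The right-hand side printed there is β0 + β1 Tx + β2 Site + β3 Missing. It has no α_j and no subscripts. Section 8 mentions no robust variance and no provider-level bootstrap, and it names no test or interval method.
- **ICC.** Protocol section 5.6: "The assumed intraclass correlation coefficient for the provider clustering effect is assumed to be 0.01". This, and the multilevel model named alongside it, belong to the sample size statement.
- **Provider volume.** Protocol section 5.3: "some providers order hundreds of screening CTs per year and other providers order only one or two".

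**The concern.** Treatment varies only between providers. If outcomes within a provider are positively correlated, a model with no provider term gives a standard error for β1 that is too small. The error runs one way: it makes a positive result look more robust to non-response than it is. This is the only missing-data sensitivity analysis written into the SAP, and its stated purpose is to test the primary conclusion.

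There is also a structural problem. A sensitivity model should give back the primary analysis when the sensitivity parameter takes its null value. This one does not, so a primary and a sensitivity result could differ for two reasons at once: the missingness assumption and the treatment of clustering.

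**Working it through.** **1. The two equations side by side.**
- Primary (section 7): β0 + α_j + β1 Treatment + β2 Site.
- Sensitivity (section 8): β0 + β1 Tx + β2 Site + β3 Missing.
- Set the sensitivity odds ratio to 1, so that β3 = 0. The sensitivity model becomes β0 + β1 Tx + β2 Site, which is the primary model without α_j.

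**2. The plan's own figure.** The plan gives no figure for this analysis. Its sample size is 270 per arm for 80% power, 9% versus 18%, ICC 0.01. A two-sided 5% test with pooled variance needs 226 per arm without clustering. With 540/300 = 1.8 patients per provider the design effect is 1 + (1.8 − 1) × 0.01 = 1.008, so n = 228, and 270 per arm gives 86.4% power. The stated target is therefore not reproduced at the average cluster size, but it errs on the safe side. That is a separate matter and does not bear on this point.

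**3. Inputs for the size of the effect.**
- 540 observed outcomes and about 300 providers (Protocol section 5.2), so m = 1.8.
- ICC 0.01 (Protocol section 5.6). ICC 0.05 is my assumption, to show what a larger value would do.
- CV of provider size 1 to 3. This is assumed; the documents give no CV.

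**4. Formula.** Design effect DE = 1 + ((CV² + 1)m − 1) × ICC. Type I error of a nominal 5% test that ignores provider = 2(1 − Φ(1.96/√DE)). The interval should be wider by √DE. Example, ICC 0.01 and CV 2: DE = 1 + (5 × 1.8 − 1) × 0.01 = 1.08, √DE = 1.039, type I error 5.9%. With equal clusters at ICC 0.01, DE = 1.008, √DE = 1.004 and type I error is 5.1%.

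**5. Simulation under no effect.**
- (a) 300 providers without pair matching, 20,000 trials per cell, test ignoring provider.
- (b) 300 providers pair-matched on volume, quit rate 13%, 40% of 1,350 outcomes observed at random (0.40 × 1,350 = 540), observed cases only, no provider term, 3,000 trials per cell.
- (c) As (b), but the unobserved outcomes are imputed 20 times from a single-level model with sensitivity odds ratio 1 and combined by Rubin's rules. Site is omitted.

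| ICC | CV | DE | √DE | Formula | (a) | (b) | (c) |
|---|---|---|---|---|---|---|---|
| 0.01 | 1 | 1.026 | 1.013 | 5.3% | 5.6% | 5.2% | 5.2% |
| 0.01 | 2 | 1.080 | 1.039 | 5.9% | 5.8% | 5.6% | 5.8% |
| 0.01 | 3 | 1.170 | 1.082 | 7.0% | 7.1% | 6.0% | 6.1% |
| 0.05 | 1 | 1.130 | 1.063 | 6.5% | 7.3% | 7.5% | 7.0% |
| 0.05 | 2 | 1.400 | 1.183 | 9.8% | 10.2% | 10.8% | 10.7% |
| 0.05 | 3 | 1.850 | 1.360 | 15.0% | 14.7% | 15.4% | 14.8% |

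Other pair-matched simulations gave about 5–6% at ICC 0.01, and 6.5–13% at ICC 0.05. Columns (b) and (c) nearly coincide: imputing the missing outcomes adds almost nothing to the inflation.

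**6. Change in the meaning of the odds ratio.** The conditional odds ratio for 18% versus 9% is (0.18/0.82)/(0.09/0.91) = 2.22. An ICC of about 0.01 corresponds to a provider SD of about 0.30 on the logit scale. The usual logistic-normal approximation divides the log odds ratio by √(1 + 0.346 × 0.30²) = 1.015, so 0.797/1.015 = 0.785, an odds ratio of 2.19. At SD 0.68 (ICC about 0.05) the result is 2.10.

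**The case against.** **The equation may be shorthand.** It follows a statement that a method will be adapted, it has no subscripts, and it models smoking where the text speaks of cessation. Section 7 says clustering will be handled by a random intercept, and the table of analyses does so wherever a model is given. This is a fair reading, but section 8 does not state it. The primary equation in the same SAP is written out in full, and an analyst who follows section 8 literally fits an unclustered model.

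**At the planned ICC the effect is close to nominal.** This stands. Average clusters are small, and even uneven ones move the error rate little. The contrast in Protocol section 5.3 concerns screening CTs ordered per year, not eligible smokers per provider, so a CV as high as 3 is an assumption.

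**Two stronger readings are tempting and not supported.**
- A reader might infer that clustering matters much more here than in the primary analysis because patients without an outcome return: up to 1,350 approached over 300 providers is 4.5 each, against 1.8. But those patients have no observed outcome. The Missing coefficient is a sensitivity parameter, set by the analyst. With it fixed, those rows add nothing to the likelihood, and if they are imputed, the between-imputation variance offsets the apparent gain. Nor are 540 and 1,350 the plan's sizes for the two analyses, since the SAP builds the primary outcome from survey and EMR data.
- A reader might infer that dropping α_j visibly shifts the odds ratio by turning a provider-specific effect into a population-averaged one. At the planned ICC the shift is from 2.22 to 2.19, which is negligible.

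**Conclusion.** The omission is real. The one model printed to test the primary conclusion under non-ignorable missingness lacks the term that represents the randomised unit, and it does not contain the primary model as a special case.

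Its size is modest. At ICC 0.01 with about 540 observed outcomes, type I error is about 5–6% for CV 1 to 3, or 7.0–7.1% at CV 3 where the pair matching is ignored. At an assumed ICC of 0.05, five times the planned value, it is about 6.5–13%, and about 15% at CV 3 in some calculations. These figures rest on the assumed CVs, on 300 providers, and on 540 as the number of observed outcomes. The documents do not give the number once EMR data are added.

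It does not follow that the primary result is at risk: the primary model and its test are unaffected. Priority is low to moderate, justified by the inconsistency and the trivial cost of removing it.

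**What to change.** In SAP section 8, add α_j ~ N(0, σ²) for provider, with patient and provider subscripts, so that the right-hand side reads β0 + α_j + β1 Tx + β2 Site + β3 Missing. Put the same term in any imputation step used to fit the model. State that the test and interval method are those of the primary model. Primary and sensitivity results then differ only in the missingness assumption, and setting the sensitivity odds ratio to 1 gives back the primary model.

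A provider-level bootstrap or a cluster-robust variance would repair the standard error, but would not make the two models nest. If the printed equation was meant as shorthand, one sentence saying that α_j carries over is enough.

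The cost is one term in the formula and the code, with no new data and no change in sample size. At ICC 0.01 and 1.8 patients per provider, intervals widen by a factor of about 1.004 with equal clusters and 1.04 at CV 2.

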The difference in risks associated with behavioral counseling between the unstructured and proactive arms are minor. In the unstructured arm, patients receive about cessation counseling by their provider and are provided with the VA Quitline's telephone number ([name]) as a free resource for telephone counseling. In the proactive arm, subjects are proactively contacted by telephone counselors to receive this same support. The proactive counseling calls may be associated with the following risks: 1) annoyance from proactive counseling outreach, or 2) increased anxiety or worry related to discussions around lung cancer screening results and smoking cessation with VA Quitline telephone counselors. We will mitigate this risk by having the VA Quitline caller remind subjects that participation in the proactive calls is voluntary. Notably, in the pilot study 89% of Veterans indicated they were completely or somewhat satisfied with the proactive telephone counseling calls, with 1 individual reporting they were neither satisfied or dissatisfied, and 2 participants declining to respond.

The difference in risks associated with pharmacotherapy support between the unstructured and proactive arms is also minimal. Although guidelines indicate all smokers should be offered pharmacotherapy support at every visit, this happens infrequently. A recent review found that only 7.6% of current smokers received a cessation pharmacotherapy order

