5.2 Recruitment Methods

Number of Subjects Needed.

Patients. We will assess CDW and CAPRI/JLV records for up to 15,000 patients (~10,000 to identify retrospective LCS orders, and ~5,000 to identify prospective LCS orders) who were offered lung cancer screening at NY Harbor and Providence to identify potential provider participants. Of these subjects, only current smokers will be approached. We anticipate approaching up to 1,350 eligible potential subjects (mailing them a study invitation packet) to invite them to participate in the survey. In order to ensure non-missing data are available on a sufficiently powered study sample, recruitment will continue until 270 subjects have completed the 12-month assessment survey in each of the care arms (total target n = 540).

Providers. We expect to recruit approximately 300 providers, 180 from Providence, RI and 120 from NY Harbor, in order to reach 540 patients (completed surveys).

Identification and Recruitment of Subjects.

Providers. We will obtain a Waiver of Informed Consent for recruitment to facilitate the identification of primary care providers ordering LCS CT scans at the NY Harbor and Providence VAs. At the beginning of the study, the study team will examine historical CDW data to identify providers who have previously ordered LCS tests. Providers who meet eligibility will then be contacted via mail, then email, and finally by Lync/Skype for Business instant message and given the recruitment materials. Any new providers who are hired at VA NY Harbor or Providence and are eligible to order a LCS CT scan, who were not identified by the historical review, will be similarly recruited when they are first identified.

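### The MNAR check uses one missingness parameter for both arms and states no impute-and-refit step, so it cannot test non-response that is informative in one arm only

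*SAP*

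**What the plan says.** SAP section 8 states: "The primary analysis will be a complete-case analysis among those who have a smoking status at 12 months". The one sensitivity analysis it gives for non-ignorable missingness is a logistic model with an intercept, treatment, site and a Missing indicator. The coefficient of Missing is described as "a sensitivity parameter representing the odds ratio of smoking cessation between people with missing outcomes and people without missing outcomes".

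The section has no treatment-by-Missing term, no values for the parameter, and no account of how missing outcomes are generated or how the treatment effect is then re-estimated. The provider random intercept of the primary model (SAP section 7) is also absent. The left side of the equation is the probability of smoking, although the parameter is defined for cessation.

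On the amount of missing data, the SAP adds: "We will examine whether there is differential missingness in outcomes across treatment arms and sites". Protocol section 5.6 expects balance: "We do not anticipate differential missing data across study arms". It also plans a secondary analysis in which "patients who do not participate in the survey assessment (e.g. missing abstinence outcomes) will be considered continued smokers". The SAP does not carry that analysis. The primary outcome is "Constructed from 12-month survey and EMR data" (SAP section 5).

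**The concern.** A complete-case result needs a check that could fail. The obvious threat is that the intervention helps patients whose 12-month status is known and does little for those whose status is missing. This means that missing and observed patients differ by more in the proactive arm than in the unstructured arm, and a single shared parameter cannot express it.

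The design makes such a pattern plausible. Only proactive patients receive the notification letter and Quitline calls, and Protocol section 5.1 lists "annoyance from proactive counseling outreach" as a risk of those calls. Proactive providers also receive assignment emails, chart notes and prescribing reminders, while unstructured providers are not notified. The recording of smoking status in the EMR could therefore differ by arm too.

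If missingness is balanced, the planned check will show almost no change. Readers would take this as robustness to informative non-response, although the check did not examine the pattern that matters.

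**Working it through.** **Inputs.** Abstinence among patients with known status is 18% proactive and 9% unstructured, with 270 observed per arm (Protocol sections 3.0 and 5.6). The plan attaches no figure to this sensitivity analysis. Its hypothesised relative risk of 2 corresponds to a complete-case odds ratio of (0.18/0.82)/(0.09/0.91) = 2.22, 95% CI 1.32 to 3.73.

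The documents give no missing share for the combined survey and EMR outcome. Protocol section 5.2 says "We anticipate approaching up to 1,350 eligible potential subjects" to obtain 540 completed surveys. So 1 − 540/1,350 = 60% is a ceiling from the survey alone, and 20% to 60% is shown as an assumed range.

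**Step 1: the model as printed.** Patients with Missing = 1 have no outcome and contribute nothing to the likelihood. For everyone else β3 × Missing = 0. The estimate of β1 is therefore the complete-case estimate of that same model for any fixed β3. In a simulation of 1,350 patients with 30/30, 30/50 and 60/60% missing, β1 matched the complete-case value to four decimals at sensitivity odds ratios of 0.1, 0.2, 0.5, 1 and 3.

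**Step 2: impute, then refit without Missing.** Let k be the cessation odds ratio of missing versus observed patients, m the missing share and p the observed rate. Then:

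- rate among the missing: p_miss = kp/(1 − p + kp)
- whole-arm rate: q = (1 − m)p + m·p_miss
- delta-method variance of logit q: [(dq/dp)/(q(1 − q))]² × p(1 − p)/270, with dq/dp = (1 − m) + m·k/(1 − p + kp)²

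**Step 3: shared k, equal missingness.** The largest departure for k between 0 and 1 is at k = 0, which is missing = smoker. At m = 60%, q = 0.4 × 0.18 = 0.072 and 0.4 × 0.09 = 0.036, so the odds ratio is (0.072/0.928)/(0.036/0.964) = 2.08.

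**Step 4: different k by arm.** Let patients with missing status quit at 9% in both arms. Control k is then 1 and proactive k is (0.09/0.91)/(0.18/0.82) = 0.45. At m = 40%, proactive q = 0.6 × 0.18 + 0.4 × 0.09 = 0.144, and the odds ratio is (0.144/0.856)/(0.09/0.91) = 1.70.

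| Missing, each arm | Shared k, all values 0 to 1 | Missing quit at 9% in both arms (95% CI) |
|---|---|---|
| 20% | 2.17–2.22 | 1.95 (1.16–3.28) |
| 40% | 2.12–2.22 | 1.70 (1.01–2.85) |
| 50% | 2.10–2.22 | 1.58 (0.94–2.65) |
| 60% | 2.08–2.22 | 1.46 (0.87–2.44) |

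In the shared-k column the lower confidence limit never falls below 1.28. These intervals ignore clustering. The ICC of 0.01 with 540/300 = 1.8 respondents per provider gives a design effect of 1.008, and even 1.02 changes the lower limits by at most 0.01. Multiple imputation with Rubin's rules on 49/270 versus 24/270 (complete-case odds ratio 2.27) agrees: at 40% missing, 2.22 (1.33–3.70) for shared k = 0.2 and 1.74 (1.04–2.92) for 9% in both arms.

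**Step 5: shared k, unequal missingness.** With 30% missing in control and 50% in proactive, the odds ratio is 1.94, 1.69 and 1.59 at k = 0.5, 0.2 and 0.1. With the shares reversed it is 2.50, 2.78 and 2.91.

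**Step 6: tipping points, k below 1 in the proactive arm only.** At 60% missing, significance is lost near k = 0.61 and the odds ratio reaches 1 near k = 0.14 (3% versus 9% among the missing). At 40% missing, significance is lost near 0.44. At 20% missing it survives even if every missing proactive patient smokes (1.70, p = 0.043).

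**The case against.** - **The literal reading is ungenerous.** Calling the term a sensitivity parameter implies a pattern-mixture analysis, and the equation looks like a sketch. This is fair. On that reading the missing refit step is a gap in the description. The inability to represent one-arm informative missingness comes from the shared coefficient alone, and it remains.
- **The shared parameter does respond when annoyance costs proactive responses.** Correct. With 30% missing in control and 50% in proactive, k = 0.1 gives 1.59 (0.96–2.62), which would overturn significance. But this reflects how much is missing, not a different mechanism by arm, and the protocol expects no such imbalance.
- **The mechanism may be weak.** Protocol section 5.1 reports that 89% of pilot patients were satisfied with the calls, and EMR data will fill in some survey non-responders. Both points reduce the likely size. Neither lets the planned check detect the problem.
- **The intervals depend on convention.** Those above fix the proactive k at 0.45. If the missing proactive rate is tied instead to the estimated control rate, the same point estimates carry narrower intervals that exclude 1: 1.70 (1.17–2.48) at 40% missing and 1.46 (1.10–1.94) at 60%. So the shrinkage of the estimate is firm, but loss of significance is not.
- **It is only a sensitivity analysis, and the SAP speaks of adapting a method.** True, but it then commits to one model. Arm-specific values chosen after seeing the data would carry little weight.

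**Conclusion.** The concern holds. The planned MNAR model cannot represent missing patients who differ from observed patients by different amounts in the two arms. As printed, it does not move the treatment effect at all. With equal missingness and an imputation step, it moves the odds ratio from 2.22 to 2.08 at most for k between 0 and 1. A moderate arm-specific departure gives 1.95 at 20% missing and 1.46 at 60%. The protocol's missing = smoker analysis is the limit of the same shared parameter, so it has the same blind spot.

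The figures assume 18% versus 9% observed, 270 observed per arm and a missing share between 20% and 60%. At the low end the conclusion is safe. A null point estimate needs an extreme case. This does not show that the trial's result would reverse, only that the stated check could not show it. It should be fixed, and the primary estimate and test are unaffected.

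**What to change.** Replace the model in SAP section 8 with one written for cessation, so that the parameter acts in the direction stated:

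logit P(quit) = β0 + α_j + β1·Tx + β2·Site + δ0·Missing·(1 − Tx) + δ1·Missing·Tx

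- Fix exp(δ0) and exp(δ1) on a grid named in advance that includes equal and unequal values, for example 0.2 to 1 in each arm.
- Multiply impute the missing outcomes from this model, refit the primary random-intercept model without the Missing terms, and pool.
- Report the odds ratio and confidence interval over the grid, the values at which the interval first includes 1, and those at which the odds ratio reaches 1.
- Carry the protocol's missing = smoker analysis into the SAP as the corner where both odds ratios go to 0.
- Report the share still missing in each arm after EMR data are added, so that readers can place the result on the grid.

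The shared-parameter analysis is kept as the diagonal of the grid. The cost is SAP wording and modest extra programming, with no new data and no change to the primary analysis or its test.
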